6.3.2 Non-measureable disease

All other lesions (or sites of disease), including small lesions and bone lesions, are considered non-measurable disease.

6.3.3 Target lesions

All measurable lesions up to a maximum of 2 lesions per organ and 5 lesions in total, representative of all involved organs should be identified as target lesions and recorded and measured at baseline. Target lesions should be selected on the basis of their size (lesions with the longest diameter) and their suitability for accurate repeated measurements (either by imaging techniques or clinically). A sum of the longest diameter (LD) for all target lesions will be calculated and reported as the baseline sum diameters. The baseline sum diameters will be used as reference by which

to characterize the objective tumor. Pathological lymph nodes: nodes with a short axis of ≥ 15 mm are considered measurable and assessable as target lesions. The short axis measurement should be included in the sum of lesions in calculation of tumor response. Nodes that shrink to < 10 mm short axis are considered normal.

6.3.4 Non-target lesions

All other lesions (or sites of disease) should be identified as non-target lesions and should also be recorded at baseline. Measurements of these lesions are not required, but the presence or absence of each should be noted throughout follow-up.

6.4 Evaluation of response to therapy

The following criteria (RECIST version 1.1) will be used to define disease response to therapy based upon radiographic measurements using contrast-enhanced CT or MRI imaging with contiguous cuts of 10 mm or less in slice thickness:⁴¹

Table 8: Definitions & Evaluation of Response

Evaluation of Target Lesions	
Complete Response (CR)	Disappearance of all target lesions.
Partial Response (PR)	At least a 30% decrease in the sum of diameters of target lesions, taking as reference the baseline sum diameters.
Progressive Disease (PD)	At least a 20% increase in the sum of diameters of target lesions, taking as reference the smallest sum recorded on study AND an absolute increase in the sum of at least 5 mm OR the appearance of one or more new lesions.
Stable Disease (SD)	Neither sufficient shrinkage to qualify for PR nor sufficient increase to qualify for PD, taking as reference the smallest sum of diameters while on study
Evaluation of Non-Target Lesions	
Complete Response (CR)	Disappearance of all non-target lesions and normalization of tumor marker level.
Incomplete Response/ Stable Disease (SD)	Persistence of one or more non-target lesion(s) or/and maintenance of tumor marker level above the normal limits.
Progressive Disease (PD)	Appearance of one or more new lesions and/or unequivocal ¹ progression of existing non-target lesions ² .

¹ For unequivocal progression on the basis of non-target disease, there must be an overall level of substantial worsening in non-target disease such that, even in presence of SD or PR in target disease, the overall tumor burden has increased sufficiently to merit discontinuation of therapy. The designation of overall

progression solely on the basis of change in non-target disease in the face of SD or PR of target disease will be extremely rare.⁴²

²In the uncommon scenario of a mixed response with response or stable disease in target lesion(s) but progression in non-target lesions only, assessment of overall response will be made by the treating investigator and confirmed with the Principal Investigator and DMC.

6.5 Evaluation of best overall response

At study completion, each patient's case will be reviewed to determine a best overall response to therapy. Based on RECIST, the best overall response is the best response recorded from the start of the study treatment until the end of treatment, taking into account any requirement for confirmation.^{41, 42} In general, the patient's best response assignment will depend on the achievement of both measurement and confirmation criteria. Patients with a global deterioration of health status requiring discontinuation of treatment without objective evidence of disease progression at that time should be classified as having "symptomatic deterioration." Every effort should be made to document objective tumor progression even after discontinuation of treatment. The best overall response will be defined as follows:

Table 9: Best Overall Response Definitions

Best Overall Response			
Target Lesion	Non-Target Lesion	New Lesion	Overall Response
CR	CR	No	CR
CR	Non CR/Non-PD	No	PR
PR	Non-PD	No	PR
SD	Non-PD	No	SD
PD	Any	Yes or No	PD
Any	PD	Yes or No	PD
Any	Any	Yes	PD

6.6 Confirmation of disease response or progression

The main goal of confirmation of objective response is to avoid overestimating the response rate observed. The Principal Investigator will confirm the objective response for each patient, and the confirmed responses will be reviewed by the DMC prior to reporting the results.

In cases where confirmation of response is not feasible, it will be made clear when reporting the outcome that the responses are not confirmed. To be assigned a status of PR or CR by RECIST, changes in tumor measurements must be confirmed by repeat assessments that should be performed no less than 4 weeks after the criteria for response are first met.^{41, 42} In the case of SD, follow-up

measurements must have met the SD criteria at least once after study entry at a minimum interval of 8 weeks (\pm 7 days).

6.7 Criteria for study completion

6.7.1 Phase I

The phase I portion of the study will close to accrual when the MTD is confirmed in a cohort of at least 6 patients and the additional 6 patients for the PK cohort have been enrolled. The study may also be closed prematurely if more than 1 of 3 patients at cohort Level -3 experience a DLT so that the MTD cannot be determined. At the discretion of the Principal Investigator and the DMC, the study may be terminated early for failure to enroll an adequate number of patients or for significant, unexpected toxicities.

6.7.2 Phase II

The phase II portion of the trial will be completed when all patients have been enrolled and all data for the study endpoints have been collected. At the discretion of the Principal Investigator and the DMC, the study may be terminated early for failure to enroll an adequate number of patients or for significant, unexpected toxicities.

7.0 STUDY PARAMETERS

Table 10: Schedule of Events

Assessments	Screening	Cycle 1 ²⁰				Cycles 2 & 3 ²⁰		Cycle 4+ ^{11,20}		Follow-Up ¹²	
	Baseline ¹	D1 ¹⁷	D8	D15	D22	D1	D15	D1	D15 ²¹	Off Treatment	Post-Treatment
Informed Consent	X										
History and physical ²	X	X	X	X	X	X	X	X		X	
Toxicity assessment ³	X	X	X	X	X	X	X	X		X	
WBC, ANC, hemoglobin, platelet	X	X	X	X	X	X	X	X	X ²³	X	
Electrolytes & renal function tests (Na, K, Cl, CO ₂ , BUN, Creatinine, Mg, Phos)	X	X	X	X	X	X	X	X	X ²³	X	
Liver function tests (AST, ALT, alk phos, total bilirubin)	X	X	X	X	X	X	X	X	X ²³	X	
Albumin, INR, PTT	X										
Serum chromogranin A		X ¹⁸				X		X			
Serum creatinine ⁴	X										
Urine protein/creatinine ⁵	X	X				X		X			
Serum pregnancy test ⁶	X										
EKG ¹⁹	X					X		X			
Echocardiogram or MUGA	X										
Pathology review ¹⁵	X										
Imaging ⁷	X							X		X	X
Temozolomide ⁸		X (D1-7)		X (D15-21)		X (D1-7)	X (D15-21)	X (D1-7)	X (D15-21)		
Pazopanib ⁹		Continuous daily administration beginning Cycle 1 Day 1									
Sulfamethoxazole prophylaxis ¹⁰		Administered 3 times per week while on treatment									
Drug Diary collection ²²						X		X			
Survival Follow-up										X	X
Correlative Studies¹⁴											
PK sampling (PK cohort only) ¹³		X (D1-3)									
IHC for MGMT expression ¹⁶	X										

¹ Baseline studies should be completed within 14 days of initiating treatment except for imaging, which must be within 28 days.

² A complete history and physical exam [including weight, height, vital signs (pulse, temperature, respiratory rate, blood pressure, oxygen saturation) and ECOG PS] will be

conducted at baseline. Subsequent visits require physical exam including vital signs, weight and ECOG PS.

³ Toxicity will be assessed using the NCI CTCAE version 4.03.

⁴ If serum creatinine ≥ 1.5 mg/dL, then creatinine clearance should be calculated and ≥ 30 mL/min

⁵ For baseline, patients must have urine protein to creatinine ratio < 1 OR a 24-hour urine protein < 1 g. For treatment cycles, only a urine protein/creatinine ratio is required.

⁶ Required for females of childbearing potential (within 14 days) – *see definition of child-bearing potential in Section 3.2*.

⁷ Imaging with CT or MRI (whichever test is used for a particular patient at baseline should be the same that is used throughout for disease assessment). Response will be assessed every 2 cycles (8 weeks +/- 7 days). After 1 year of protocol therapy, patients may switch to imaging every 12 weeks (+/- 7 days) per treating physician's discretion.

⁸ Temozolamide will be administered on Days 1-7(+/-1 day) and 15-21(+/-1 day) of each cycle. Please refer to Section 5.2 for further details.

⁹ Pazopanib will be administered continuously starting Cycle 1, Day 1 until study discontinuation. Please refer to Section 5.2 for further details.

¹⁰ All patients will receive prophylaxis with trimethoprim-sulfamethaxazole double strength (sulfamethoxazole 800 mg and trimethoprim 160 mg) by mouth 3 times a week.

¹¹ Patients will continue on treatment until disease progression (or until removed from study for other reasons, as outlined in Section 5.8.1).

¹² Patients removed from the study for disease progression who have no ongoing toxicity will undergo one last off-treatment visit for response. Survival follow-up will continue every 6 months for 1 year in clinic and/or via phone ; survival follow-up may occur either in clinic or via phone contact. Additional follow-up may be required for patients experiencing toxicity at the time of treatment discontinuation.

¹³ Patients in the PK cohort only will have PK samples drawn on Days 1-3 of Cycle 1. Please refer to Sections, 6.1.2.2 and 12.1 for details.

¹⁴ Correlative studies will only be done on the 6 patients in the PK cohort, as well as all patients enrolled to the phase II portion of the study.

¹⁵ Copy of pathology report is sufficient for registration. However a sample of tissue from a recent biopsy will be required for the 6 patients enrolled in the PK cohort and all patients in the phase II portion of the trial

¹⁶ Please refer to Section 12 for details regarding tissue requirements. Tissue from the most recent biopsy will be obtained for study purposes – patients will not undergo repeat biopsy for correlative studies. This applies to both PK cohort and Phase II patients

¹⁷ If baseline labs (chemistries, Mg, Phos, and CBC) were completed within 48 hours prior to start of treatment, they do not need to be repeated for Cycle 1 Day 1.

¹⁸ If serum chromogranin is completed within 14 days of treatment, it does not need to be repeated for Cycle 1 Day 1.

¹⁹ EKG will be performed at baseline (within 14 days of initiating study treatment) and then Day 1 of every cycle beginning with Cycle 2 – EKG does NOT need to be repeated at Cycle 1 Day 1.

²⁰ Assessments will be completed +/- 3 day from treatment Days 1, 8, 15, and 22 unless otherwise noted. Imaging will be assessed every 2 cycles (8 weeks +/- 7 days).

²¹ For Cycle 4 and beyond, Day 15 labs may be completed at a local facility if more convenient for patients, per treating investigator's discretion.

²² The drug diary (completed by the patient during each cycle) should be collected on Day 1 of the next cycle. Patients should be instructed to complete the drug diary every day and bring it to their visit on Day 1 of the next cycle.

²³ For patients who discontinue Temozolamide after 1 year of treatment, D15 laboratory tests (WBC, ANC, hemoglobin, platelet, Electrolytes & renal function tests [Na, K, Cl, CO₂, BUN, Creatinine, Mg, Phos] and AST, ALT, alk phos, total bilirubin) are not required to be done.

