5.2.1 Temozolomide

Patients will be instructed to take temozolomide orally once a day starting on Cycle 1 Day 1 of treatment. The dose of temozolomide will depend on the phase and cohort onto which the patient is enrolled (refer to Section 5.3 for dose escalation rules). For phase I, the starting dose of temozolomide will be 150 mg/m² per day. Patients will continue temozolomide for 7 consecutive days at a time, every other week (Days 1-7 and 15-21 of the cycle). One cycle equals 28 days. Patients will continue to take temozolomide every other week until study discontinuation (refer to Section 5.8 for duration of treatment and discontinuation rules).

Temozolomide tablets will be swallowed whole. Patients will be instructed to fast at least 1 hour before and 1 hour after administration of temozolomide. Water is allowed during the fasting period.

Temozolomide may be taken before or after pazopanib (on days when both drugs are taken), but it is recommended that they be taken around the same time. If a dose is missed, the patient should take the dose as soon as possible, but only if there are 12 or more hours remaining before the next dose is due. If the next dose is due in less than 12 hours, the subject should skip the missed dose and take the next dose as scheduled.

If vomiting occurs after taking temozolomide, the patient should not take a replacement dose on that day. The patient should resume taking temozolomide at the next scheduled dose on the following day.

(Note: For patients in the PK cohort, please refer to the Study Parameters Table for PK Cohort for information regarding temozolomide doses on Cycle 1, Days 1-3.)

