5.2.2 Pazopanib

Patients will be instructed to take pazopanib orally once a day starting on Cycle 1 Day 1 of study treatment. The dose of pazopanib will depend on the phase and cohort onto which the patient is enrolled (refer to Section 5.3 for dose escalation rules). For phase I, the starting dose of pazopanib will be 400 mg per day. Pazopanib will be taken daily continuously study discontinuation (refer to Section 5.8 for duration of treatment and discontinuation rules).

Pazopanib should be taken orally without food at least 1 hour before or 2 hours after a meal. The tablets should be swallowed whole and must not be crushed or broken. The time of day the tablets are taken should be relatively constant. Pazopanib may be taken before or after temozolomide (on days when both drugs are taken), but it is recommended that they be taken around the same time. If a dose is missed, the patient should take the dose as soon as possible, but only if there are 12 or more hours remaining before the next dose is due. If the next dose is due in less than 12 hours, the subject should skip the missed dose and take the next dose as scheduled.

If vomiting occurs after taking pazopanib, the patient should not take a replacement dose on that day. The patient should resume taking pazopanib at the next scheduled dose on the following day. If vomiting persists, the patient should be instructed to notify the investigator.

(Note: For patients in the PK cohort, please refer to the Study Parameters Table for PK Cohort for information regarding pazopanib doses on Cycle 1, Days 1-3.)

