12.0 PATHOLOGY REQUIREMENTS – CORRELATIVE STUDIES

12.1 Pharmacokinetics (PKs)

12.1.1 Timing

After determination of the MTD, the last cohort of the phase I portion will be expanded to include an additional 6 patients who will undergo PK testing to evaluate the effect of pazopanib on the pharmacokinetics of temozolomide. The MTD has now been identified at dose level -2 (75 mg/m² per day p.o. days 1-7 and 15-21 of Temozolomide and 400 mg per day p.o. days 1-28 of Pazopanib). As of 12.15.15, all patients moving forward will be treated at this dose. As stated above, the PKs are mandatory for this cohort.

The schedule and dosing for these 6 patients will be as follows:

12.1.1.1 Day 1, Cycle 1

Patients will not take either study drug prior to arriving to the clinic. Patients will have a time = 0 sample drawn, and then be instructed to take their dose of temozolomide. Patients will then have PK samples drawn at 10 min (+/-5 min), 30 min (+/-5 min), 1 hour (+/-5 min), 2 hours (+/-5 min), 3 hours (+/-5 min), 4 hours (+/-30 min), 6 hours (+/-30 min), 8 hours (+/-30 min), and

24 hours(+/- 1 hour) post-dose (drawn on Day 2. This will be the same sample as the pre-dose PK sample of Day 2 provided Day 2 drug administration is done within 1 hour of sample collection. One 3 ml sample is needed).

Pazopanib will be held on this day.

12.1.1.2 Cycle 1, Day 2:

Patients will continue to take temozolomide as instructed but will not take pazopanib until instructed to do so in clinic. Patients will have a time = 0 sample drawn and then be instructed to take their dose of pazopanib. This will be the same sample as the 24-hour post-dose PK sample of Day 1, provided Day 2 drug administration is done within 1 hour of sample collection. If this drug administration is delayed beyond one hour, then another 3 ml PK sample has to be collected for the pre-dose PK of Day 2).

Patients will then have PK samples drawn at 10 min(+/- 5 min), 30 min(+/- 5 min), 1 hour(+/- 5 min), 2 hours(+/- 5 min), 3 hours(+/- 5 min), 4 hours(+/- 30 min), 6 hours(+/- 30 min), 8 hours(+/- 30 min), and 24 hours(+/-1 hour) (done on Day 3) post-dose.

12.1.1.3 Cycle 1, Day 3:

Patients will not take either study drug prior to arriving to the clinic. Patients will have 1 PK sample drawn (the 24 hours[+/- 1 hour] post-pazopanib dose sample from Day 2) and then continue to take both temozolomide and pazopanib as instructed per protocol.

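### PK-cohort dosing instructions disagree: on Day 2, Section 12.1.1.2 leaves temozolomide unrestricted before the time-0 draw and times sampling from pazopanib; on Day 1, Table 10 omits the pazopanib hold (low severity)

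*Combined protocol and SAP*

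**What the plan says.** Section 2.1.2.2 asks for the pharmacokinetics of temozolomide alone and with pazopanib. Sections 6.1.2.2 and 9.1.2 assign temozolomide alone to Cycle 1 Day 1 and the combination to Day 2, in 6 patients at the MTD.

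**Day 2.** Section 6.1.2.2.2 places time 0 ahead of both drugs. Section 12.1.1.2 tells patients to keep taking temozolomide according to their instructions and withholds only pazopanib until clinic staff say so. It then has time 0 drawn, pazopanib given and the remaining samples collected. Sections 12.1.1.1 and 12.1.1.3, for Days 1 and 3, rule out both drugs before arrival. The Day 2 time-0 sample is normally the same tube as the Day 1 24-hour sample.

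**Day 1.** For the PK cohort, Section 12.1.1.1 states: "Pazopanib will be held on this day". The pazopanib row of Table 10 reads "Continuous daily administration beginning Cycle 1 Day 1". Footnote 9 repeats the Day 1 start, "Pazopanib will be administered continuously starting Cycle 1, Day 1 until study discontinuation", and refers to Section 5.2. Section 5.2.2 opens with "Patients will be instructed to take pazopanib orally once a day starting on Cycle 1 Day 1 of study treatment" and closes with a note for the PK cohort: "please refer to the Study Parameters Table for PK Cohort for information regarding pazopanib doses on Cycle 1, Days 1-3". Section 5.2.1 has the matching note for temozolomide. No table of that name is found in the supplied document. Footnote 13, attached to the PK sampling row, says: "Please refer to Sections, 6.1.2.2 and 12.1 for details".

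**The concern.** A within-patient comparison of Day 1 with Day 2 needs three things: no pazopanib on Day 1, a clean pre-dose sample on Day 2, and a Day 2 clock that starts at the temozolomide dose. The plan intends all three, but some of its dosing instructions do not secure them.

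Site staff could follow Section 12.1.1.2 to the letter and still draw time 0 after a temozolomide dose taken at home. That is the more important gap, because Section 12.1.1 is the detailed PK procedure. Separately, staff who dose from the Table 10 pazopanib row would give pazopanib on Day 1, and that patient would have no temozolomide-alone profile. At stake is the quality of one secondary PK comparison in 6 patients.

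**Working it through.** The plan gives no figure to reproduce. The check compares the instructions and then does simple counts.

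**Day 2**

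1. *Measured drug.* Section 6.1.2.2 describes an assay for plasma temozolomide only, and the parameters listed in 9.1.2 are for temozolomide. The relevant clock is therefore time since temozolomide.
2. *Drugs barred before the clinic draw.* Day 1 (12.1.1.1): both. Day 2 (12.1.1.2): pazopanib only. Day 3 (12.1.1.3): both. Section 6.1.2.2.2 implies both on Day 2. Section 12.1.1.2 is the exception.
3. *Is an early temozolomide dose permitted as written?* Yes. Section 5.2 makes both drugs self-administered, 5.2.1 allows temozolomide before or after pazopanib, and 12.1.1.2 adds no restriction.
4. *Effect on the shared sample.* Temozolomide taken before the draw puts second-dose drug into the last point of the Day 1 profile and into the Day 2 baseline. The Day 1 point feeds the half-life and the extrapolated AUC listed in 9.1.2.
5. *Effect on the Day 2 times.* Let temozolomide be taken x minutes before pazopanib. A draw at nominal time t after pazopanib then falls at t + x after temozolomide. It lies outside its stated window, read against temozolomide, when x exceeds the half-width of that window. The 9 post-dose draws have these windows: 10 min, 30 min, 1, 2 and 3 h at ±5 min (5 draws); 4, 6 and 8 h at ±30 min (3 draws); 24 h at ±60 min (1 draw).

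| Assumed x | First draw after temozolomide | Draws outside window |
|---|---|---|
| 5 min | 10 + 5 = 15 min | 0 of 9 |
| 10 to 30 min | 20 to 40 min | 5 of 9 |
| 31 to 60 min | 41 to 70 min | 5 + 3 = 8 of 9 |

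The documents give no value for x; the range is an assumption. The table shows how sensitive the profile is to the gap and does not predict what happened.

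**Day 1**

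1. *Overlap.* Table 10 has a PK-cohort sampling row, so it covers these patients. Its pazopanib row and footnote 9 start the drug on the day that 12.1.1.1 holds it. All 6 PK patients fall under both instructions.
2. *Dosing route.* Footnote 9 leads to Section 5.2, whose notes flag an exception but name a table not found in the supplied document.
3. *Sampling route.* Footnote 13 leads to 6.1.2.2 and 12.1, where the hold is explicit.
4. *Size if the row is followed.* A Day 1 profile is 10 draws (time 0 plus 9). One patient given pazopanib on Day 1 removes 1/6 = 16.7% of the temozolomide-alone profiles. The documents give no basis for the probability of this.

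**The case against.** The strongest reply on Day 1 is that this is a general rule with a signposted exception. The 5.2 notes say that PK-cohort dosing on Days 1-3 is different, 12.1.1.1 is unambiguous, and 6.1.2.2 and 9.1.2 agree with it. Draw times appear only in 6.1.2.2 and 12.1, so a site cannot run the Day 1 profile from Table 10 without opening a section that shows the intended dosing. This largely stands, and it is why the Day 1 conflict is a low-risk cross-reference error.

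A reader might also infer that a PK dosing table was left out of the protocol, or that the references run in a circle. The documents do not establish either. The supplied text is incomplete, and a stand-alone laboratory manual is mentioned in 12.1.4. Section 7.0 is itself titled Study Parameters, and the amendment log shows that its correlative block once carried a PK-cohort label, so the notes may use an old name for Table 10. On that reading the PK sampling row and footnote 13 lead to the hold; the circle appears only if the reader follows the general pazopanib row.

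On Day 2, it can be said that 12.1.1.2 does not tell anyone to take temozolomide before the draw, that footnote 13 cites 6.1.2.2 alongside 12.1, that Section 5.2 recommends taking the two drugs at about the same time, and that the sample log in 12.1.3 records last-dose times. The synopsis also mentions sampling for both drugs, which might explain a pazopanib clock. These points lower the risk but do not remove the contradiction. Logged times can correct the Day 2 clock; they cannot restore an uncontaminated shared sample. And the stated objective, assay and parameter list all concern temozolomide.

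**Conclusion.** The PK-cohort instructions are internally inconsistent and wrong as written, at low severity. The Day 2 gap matters more, because literal compliance with 12.1.1.2 can damage the data. The Day 1 gap is avoidable by anyone who follows footnote 13. The exposure is limited to objective 2.1.2.2, an analysis that 9.1.2 calls descriptive, in 6 patients.

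Three stronger conclusions should not be drawn:

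- **That the PK design is flawed.** Temozolomide alone on Day 1 and the combination on Day 2 is clear from 6.1.2.2, 9.1.2 and 12.1.1.
- **That losing one patient defeats the Wilcoxon signed rank test.** The smallest exact two-sided p is 2/2^6 = 0.031 with 6 pairs and 2/2^5 = 0.063 with 5, so significance at 0.05 would be out of reach with 5 pairs but not at 0.10. The plan states no significance level for this comparison.
- **That patients were misdosed, or that the main results are affected.** The documents report no such event. The MTD rests on DLTs, and the ORR and the Simon rule rest on tumor response; none of these uses the PK profiles.

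The Day 2 window counts hold only under the assumed dosing gap.

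**What to change.** 1. **Section 12.1.1.2:** state that neither drug is taken before arrival, that time 0 is drawn before both drugs, that both are then taken together in clinic, and that draws are timed from the temozolomide dose. The label of the Day 3 sample in 12.1.1.3 should follow.
2. **Table 10, pazopanib row and footnote 9:** add *except PK cohort: hold on Cycle 1 Day 1, first dose Day 2; see 6.1.2.2 and 12.1.1*.
3. **Notes in 5.2.1 and 5.2.2:** refer to Sections 6.1.2.2 and 12.1.1 in place of the named table.

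Pointing the notes to 12.1.1 without the first change would send staff to the weaker Day 2 instruction.

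The cost is wording in five places plus the Day 3 label, with no new visit, sample or analysis. The change helps only PK patients not yet treated. All patients have been treated at the MTD dose since 12.15.15 and this version is dated January 24, 2018; the documents do not say how many PK patients remain. For any already sampled, the analysis should use the logged temozolomide times and flag each shared sample drawn after a Day 2 temozolomide dose.
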